7.18.9 Intraocular pressure

The intraocular pressure (IOP) will be measured using air tonometry.

7.18.10 Optical coherence tomography (OCT)

Anterior segment OCT and fundus OCT will be taken as per the standard clinical practise. The findings will be recorded in the source documentation as either normal or abnormal. In case of abnormal findings the observation will be evaluated as clinical significant or not clinically significant.

7.18.11 Quality of life questionnaire

The questionnaire will be explained to the patient and handed over by staff. The translated version is enclosed in the Appendix 1.

7.18.12 Spectacle independence questionnaire

The questionnaire will be explained to the patient and handed over by staff. The translated version is enclosed in the Appendix 2.

7.19 Equipment

The equipment for assessing the clinical investigation variables is to the discretion of the investigator and his standard of care. The technicians and investigators should be familiar with the instructions for use of the devices and have prior experience with the devices before using it at the subject. The maintenance and (if applicable calibration) of the equipment shall be performed as required by the instructions for use.

7.20 Monitoring

A designated clinical monitor will oversee the clinical investigations in accordance with our established processes and applicable health authority regulations. The monitoring process will encompass the following components:

- The clinical trial monitor may conduct meetings with investigators before the start of the clinical investigation to evaluate the suitability of the subject population, facilities, and equipment in relation to the study requirements. These meetings also serve to familiarize the investigators with the clinical investigational plan.
- The clinical trial monitor may meet with the investigator(s) when subjects are being enrolled to ensure proper subject selection and accurate data recording.
- Throughout the clinical investigation, the clinical trial monitor retains the authority to visit the clinical site at any given time to review worksheets, eCRFs, and regulatory documents pertaining to the clinical investigation.
- Interim monitoring visits and telephone consultations will be carried out as necessary during the course of the clinical investigation to ensure satisfactory progress and comprehensive documentation of findings.
- Source Data Verification will be performed using a risk-based approach, with a

 PERFECT LENS PL-RIS01	Clinical Investigation Plan	Page no.	40 z 55
		Version	02
		Date	2023-07-18

particular emphasis on primary and key secondary endpoints, as well as safety considerations. This verification process will be supported by remote monitoring. Detailed information regarding these procedures can be found in the Monitoring Plan.

- The clinical trial monitor has the prerogative to visit the clinical site at any time during the investigation to review worksheets, eCRFs, regulatory documents related to the clinical investigation, and patient source data records.
- Interim monitoring visits and telephone consultations will be conducted as required throughout the clinical investigation to ensure appropriate progress and comprehensive documentation of findings. Additional specifics can be found in the Monitoring Plan.

7.21 End of clinical investigation

The end of the clinical investigation is defined as the last patient last visit. Competent Authorities and all other applicable parties will be informed within 15 days after the end of the clinical investigation.

 PERFECT LENS PL-RIS01	Clinical Investigation Plan	Page no.	41 z 55
		Version	02
		Date	2023-07-18

8 Statistical consideration

8.1 Sample size

A total of up to 24 eyes from 12 patients will be enrolled in this clinical investigation. Since this is a pilot clinical trial there is no proper sample size calculation performed. The number of the patients is chosen based on the estimated recruitment rate in the study duration and recommendation for pilot clinical trial in the literature ¹.

8.2 Statistical analyses

Due to the nature of the study only descriptive statistical will be provided for the parameters in the final report.

The default summary statistics for quantitative variables will be the number of observations (n), number of missing observations (Nmiss), arithmetic mean, standard deviation (SD), median, minimum (min) and maximum (max) for those patients with data available.

For qualitative variables, the number (n) and percentage (%) of patients with non-missing data per category will be the default summary presentation, and where appropriate and present, the number of missing values as a separate category (Nmiss). For questionnaires, the missing values will be evaluated in an additional category of the variable.

Percentages will be calculated using a denominator of all patients in a specified population or Treatment group with available data. For questionnaires, the percentage will be based on all subjects in the respective Treatment arm attending the visit. If necessary, the denominator will be specified in a footnote to the tables for clarification.

The visual acuity data will be except the above mentioned characteristics also shown in cumulative frequency charts.

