	
There are three co-primary effectiveness endpoints at the 1-month post Treatment visit.
 
Distance Corrected Near Visual Acuity (DCNVA) at 40 cm. The hypothesis tested for is to demonstrate superiority of the near vision of treated IOL to the near vision provided by the pre-Treatment IOL.
 
Distance Corrected Intermediate Visual Acuity (DCIVA) at 66 cm. The hypothesis tested for is to demonstrate non-inferiority of the treated IOL to the pre-treated IOL (using a non-inferiority margin of 0.10 logMAR).
 
Best corrected distance visual acuity (CDVA) at 4m. The hypothesis tested is to demonstrate non-inferiority of the treated IOL to the pre-Treatment IOL for corrected distance vision (using a non-inferiority margin of 0.10 logMAR).
								
Other outcome measures	
The following is a list of additional outcomes measures:
 
Uncorrected and corrected distance visual acuity (UDVA)
 
Uncorrected and corrected intermediate visual acuity at 66 cm (UIVA)
 
Uncorrected near visual acuity at 40 cm (UNVA)
 
Corrected near visual acuity at 40 cm (CNVA)
 
Defocus curve
 
Contrast sensitivity
 
Subjective manifest refraction
 
Slit Lamp examination findings
 
Fundus examination findings
 
Intraocular pressure
 
Spectacle independence questionnaire
 
QoV patient questionnaire
 
Treatment satisfaction
 
Adverse Events
 
Device deficiency
								
Examination schedule	
 
 Preoperative	Day -60 to day -1	
 
 Surgery visit	Day 0	
 
 Postoperative 1 week	Days 5 to 9	
 
 Postoperative 1 month	Days 21 to 42	
 
	Preoperative	Day -60 to day -1	Surgery visit	Day 0	Postoperative 1 week	Days 5 to 9	Postoperative 1 month	Days 21 to 42
Preoperative	Day -60 to day -1								
Surgery visit	Day 0								
Postoperative 1 week	Days 5 to 9								
Postoperative 1 month	Days 21 to 42								

 PERFECT LENS	Clinical Investigation Plan	Page no.	10 z 55
		Version	02
PL-RIS01		Date	2023-07-18

	Postoperative 3 months	Days 70 to 98
Sample size	A total of up to 24 eyes from 12 patients will be enrolled in this clinical investigation.	

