Statistical analyses	The study will use descriptive statistics to summarize quantitative and qualitative variables in the final report. For quantitative variables, it will provide measures such as mean, median, standard deviation, minimum, and maximum. For qualitative variables, it will present the number and percentage of patients in each category, including missing data.	

 PERFECT LENS PL-RIS01	Clinical Investigation Plan	Page no.	11 z 55
		Version	02
		Date	2023-07-18

3 Administrative structure

PRINCIPAL INVESTIGATORS: [name], PhD, FEBOS-CR
 Gemini Eye Clinic
 [name]
 Zlín, Czech Republic

DEVICE OPERATION: [name]
 Perfect Lens, LLC
 [name]
 [name]

[name]
 Perfect Lens, LLC
 [name]
 [name]

MEDICAL MONITOR: [name].
 [name]
 [name]

DATA MONITOR: [name]
 Perfect Lens, LLC
 [name]
 [name]

STUDY MONITOR: [name]
 [name]
 Zlín, Czech Republic

SPONSOR: [name]
 Perfect Lens LLC
 [name]
 [name]

CONFIDENTIAL

 PERFECT LENS PL-RIS01	Clinical Investigation Plan	Page no.	12 z 55
		Version	02
		Date	2023-07-18

4 Identification and description of the investigational device

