7.1 Study design

This is a prospective non-randomized patient controlled single centre design pilot clinical trial. One Study Cohort is planned with up to 12 patients and up to 24 eyes. The post Treatment eyes will be compared to the pre-Treatment eyes to determine if endpoints have been met. The study will treat both eyes of a patient to ensure that the patient has effective multi focal vision. The Treatment for both eyes may be on the same day, assuming there are no issues with the first Treatment.

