7.2 Endpoints

There are three co-primary effectiveness endpoints at the 1-month post Treatment visit.

Distance Corrected Near Visual Acuity (DCNVA) at 40 cm. The hypothesis tested for is to demonstrate superiority of the near vision of treated IOL to the IOL pre-Treatment.

Distance Corrected Intermediate Visual Acuity (DCIVA) at 66 cm. The hypothesis tested for is to demonstrate non-inferiority of the treated IOL to the pre-treated IOL (using a non-inferiority margin of 0.10 logMAR).

Best corrected distance visual acuity (CDVA) at 4m. The hypothesis tested for the co-primary effectiveness endpoint #3 is to demonstrate non-inferiority of the treated IOL to the pre-Treatment IOL (using a non-inferiority margin of 0.10 logMAR).

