7.12 Post-Operative 1 Month Visit

This visit should occur at postoperative days 21-42. The following information will be captured for the study eye at this visit:

- 1. Record changes in medical/ocular history and ocular and non-ocular concomitant medications
- 2. The following tests shall be performed:
 - a) Measure monocular and binocular uncorrected distance visual acuity (UDVA);
 - b) Measure monocular and binocular corrected distance visual acuity (CDVA)
 - c) Perform Manifest Refraction
 - d) Measure monocular and binocular uncorrected near vision acuity (UNVA) at 40 CM,
 - e) Measure monocular and binocular distance corrected near vision acuity (DCNVA) at 40cm,
 - f) Measure monocular and binocular uncorrected intermediate vision acuity (UIVA) at 66cm,
 - g) Measure monocular and binocular distance corrected intermediate vision acuity (DCIVA) at 66 cm
 - h) Perform slit lamp biomicroscopy
 - i) Perform fundus Exam
 - j) Perform tonometry to measure IOP
 - k) Collect a defocus curve for patient's vision
 - l) Collect mesopic and photopic contrast sensitivity (with and without glare)

 PERFECT LENS PL-RIS01	Clinical Investigation Plan	Page no.	32 z 55
		Version	02
		Date	2023-07-18

- m) Adverse Events assessment

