7.16.1 Subject withdrawal or discontinuation

Subject participation is voluntary; any subject may discontinue participation in the clinical The clinical investigation will be conducted without prejudice, and subjects have the option to withdraw from the study voluntarily or be withdrawn by the Investigator or Sponsor. The Investigator has the authority to terminate subjects from the clinical investigation only if their continued participation in the study Treatment regimen would pose a risk to their health

 Clinical Investigation Plan PL-RIS01	Page no.	34 z 55
	Version	02
	Date	2023-07-18

and/or welfare. Efforts will be made to encourage subjects who wish to withdraw their consent to return to the clinical site for an exit visit assessment before officially withdrawing.

Subjects may be discontinued from the clinical investigation only when there are no other viable options. Reasons for discontinuation include, but are not limited to:

- Screen failure
- Subject's withdrawal of consent prior to Treatment
- Inability to continue participating in the study
- Subject's death
- Subject discontinued by the investigator (e.g., inadequate dilation on the surgical day)

A subject exit form must be completed for all subjects who complete, discontinue, or are terminated from the clinical investigation, providing the reason for their exit. Discontinued subjects will still be included in the analysis up until the point of their exit. Whenever feasible, all necessary clinical assessments will be conducted before the subject exits the investigation, even if the assessment was not originally scheduled for that particular visit.

The subject numbers assigned to discontinued subjects will not be reassigned to new participants.

Discontinued subjects will not be replaced, except in cases where they discontinued before receiving study Treatment.

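### Three co-primary hypotheses are announced as tested, two against a 0.10 logMAR margin, but the analysis plan allows only descriptive statistics

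*Protocol*

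**What the plan says.** **Hypotheses.** The Protocol synopsis (Primary endpoints) and section 7.2 name three co-primary effectiveness endpoints at the 1-month visit. For DCNVA at 40 cm the synopsis gives the aim as "to demonstrate superiority of the near vision of treated IOL to the near vision provided by the pre-Treatment IOL". For DCIVA at 66 cm, section 7.2 gives it as to "demonstrate non-inferiority of the treated IOL to the pre-treated IOL (using a non-inferiority margin of 0.10 logMAR". CDVA at 4 m has the same form and the same margin. Each of the three is described as a hypothesis that is tested.

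**Decision.** Section 7.1: "The post Treatment eyes will be compared to the pre-Treatment eyes to determine if endpoints have been met".

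**Analysis.** Section 8.2: "Due to the nature of the study only descriptive statistical will be provided for the parameters in the final report". The outputs listed are n, number missing, mean, SD, median, minimum and maximum, counts and percentages, and cumulative frequency charts for visual acuity. The statistical row of the synopsis agrees: "The study will use descriptive statistics to summarize quantitative and qualitative variables in the final report".

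**Size.** Section 8.1 plans up to 24 eyes from 12 patients and states: "Since this is a pilot clinical trial there is no proper sample size calculation performed".

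**The concern.** A non-inferiority hypothesis is settled by setting an interval or a test against the margin, and a superiority hypothesis by setting one against zero. Section 8.2 provides neither. The 0.10 logMAR margin appears in the endpoint definitions and is used nowhere else.

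An analyst who follows 8.2 to the letter cannot deliver the determination promised in 7.1. An analyst who tests the hypotheses departs from 8.2. The practical risk is that a mean change is reported descriptively and then presented as having met an endpoint, or that the choice between describing and claiming is made once the results are known. CDVA matters most here: section 6.2.3 concedes that splitting light may cost some contrast or acuity, while section 6.1 anticipates near vision with no loss of far vision.

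**Working it through.** **1. Text comparison.** The protocol states no alpha, power, SD or derived sample size, so there is no figure of its own to reproduce. The check is whether any stated output can decide any stated hypothesis.

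| Endpoint (1 month) | Hypothesis in synopsis and 7.2 | Needed to decide it | Provided in 8.2 or synopsis |
|---|---|---|---|
| DCNVA, 40 cm | Superiority to pre-Treatment | Interval or test against 0 | None |
| DCIVA, 66 cm | Non-inferiority, 0.10 logMAR | Interval or test against 0.10 | None |
| CDVA, 4 m | Non-inferiority, 0.10 logMAR | Interval or test against 0.10 | None |

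Section 8.2 neither names nor forbids a change score. A mean change without an interval would still not establish non-inferiority.

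**2. Illustration: how far a bare mean can mislead.** Assumptions not in the protocol: two-sided 95% level, one value per patient, paired change (1 month minus pre-Treatment, positive = loss in logMAR), SD of change 0.06 to 0.15. From the protocol: n = 12 (8.1), margin 0.10 (7.2).

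- Half-width = t(0.975, n−1) × SD / √n
- Largest observed mean loss that still excludes the margin = 0.10 − half-width

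For n = 12, t = 2.201. At SD 0.10: 2.201 × 0.10 / √12 = 0.0635, and 0.10 − 0.0635 = 0.0365.

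| SD of change | Half-width, n = 12 | Largest passing mean loss, n = 12 | Half-width, n = 10 |
|---|---|---|---|
| 0.06 | 0.0381 | 0.0619 | 0.0429 |
| 0.08 | 0.0508 | 0.0492 | 0.0572 |
| 0.10 | 0.0635 | 0.0365 | 0.0715 |
| 0.15 | 0.0953 | 0.0047 | 0.1073 |

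At SD 0.10 and n = 12, an observed mean loss of 0.05 lies inside the margin, yet its upper limit is 0.05 + 0.0635 = 0.1135, which fails.

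The n = 10 column (t = 2.262) supposes that two treated patients are lost. That is hypothetical, since the protocol states no loss rate, but section 7.16.1 says "Discontinued subjects will not be replaced, except in cases where they discontinued before receiving study Treatment". At SD 0.15 and n = 10, even an observed mean loss of zero would not exclude the margin.

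**3. Power if the hypotheses are kept.** Noncentral t, one-sided 0.025, n = 12, noncentrality (0.10 − true loss) / (SD / √12). The joint value is the square of the single value, which assumes the two non-inferiority endpoints are independent.

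| SD | One endpoint, true loss 0 | Both, true loss 0 | One endpoint, true loss 0.05 | Both, true loss 0.05 |
|---|---|---|---|---|
| 0.06 | 0.999 | 0.999 | 0.748 | 0.560 |
| 0.08 | 0.975 | 0.952 | 0.506 | 0.256 |
| 0.10 | 0.883 | 0.780 | 0.353 | 0.124 |
| 0.15 | 0.558 | 0.311 | 0.183 | 0.033 |

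With correlated changes (SD 0.10, 400,000 simulated trials), joint power with true loss 0 and 0.05 is 0.803 and 0.191 at correlation 0.5, and 0.831 and 0.251 at correlation 0.8. At n = 10 and SD 0.10, the single-endpoint values are 0.803 and 0.293, and the independent joint values 0.645 and 0.086. Requiring DCNVA superiority as well can only lower the joint figures; by how much depends on a true gain that the protocol does not state.

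**The case against.** The best defence is that this is openly a small, single-arm pilot with no alpha, power or success rule, that no stopping rule or clinical step depends on the hypotheses, and that 8.2, the operative analysis section, is already the cautious one. On that view the hypothesis wording is loose language that can simply be deleted. Pilot status does justify a descriptive analysis and the absent sample size calculation. It does not explain stating superiority and non-inferiority hypotheses with a margin, or undertaking in 7.1 to decide whether the endpoints are met.

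A second defence is that 8.2 calls its list a default, that an interval can count as descriptive, and that section 11 plans per-protocol cohorts for evaluating the primary endpoints, so some detail evidently lies elsewhere, perhaps in an SAP. None of this supplies an interval, a test or a margin rule. The word *only* in 8.2 also means that an SAP adding a non-inferiority test would contradict 8.2, while one without it would leave 7.2 unmet.

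It is fair to say that the numbers illustrate the defect and do not prove it. They rest on an assumed SD, level and unit of analysis, and at SD 0.06 power with no true loss is ample. The choice between monocular and binocular values and the handling of paired eyes are conditions of one remedy, not separate faults.

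**Conclusion.** The concern holds and must be fixed. The protocol contradicts itself on all three co-primary endpoints: as written, no formal superiority or non-inferiority conclusion can be drawn on any of them, although the protocol says it will determine whether they are met. This follows from the text alone and needs no assumption.

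The size of the practical risk does depend on assumptions. Over SDs of 0.06 to 0.15 logMAR, with 12 patients as the unit and a two-sided 95% level, the uncertainty around a mean change is about 38% to 95% of the margin (0.038/0.10 to 0.095/0.10). A point estimate alone would hide this.

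**What to change.** Choose one option before any outcome data are seen.

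**(a) Keep the pilot descriptive**, which fits 8.1 and 8.2. Remove the hypothesis, superiority and non-inferiority wording and the margins from the synopsis and 7.2, reword the sentence in 7.1 about endpoints being met, and make no such claim in the report. *Cost:* wording only. The sponsor gives up any superiority or non-inferiority claim from this study.

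**(b) Keep the hypotheses.** Amend 8.2 and the synopsis so that each co-primary is analysed as the paired change (1 month minus pre-Treatment) with a two-sided 95% confidence interval. DCNVA is superior if the upper limit is below 0; DCIVA and CDVA are non-inferior if the upper limit is below +0.10 logMAR; all three are required for success. Fix in advance whether the monocular or the binocular value decides. Either is acceptable, and both are collected at 1 month (for DCNVA, section 7.12: "Measure monocular and binocular distance corrected near vision acuity (DCNVA) at 40cm"). If eyes are the unit, allow for within-patient correlation. State that the study was not sized for these tests. *Cost:* a few sentences and no new data, patients or procedures, but a real chance of failing for lack of precision. With 12 patients, independent joint power for the two non-inferiority endpoints runs from 99.9% (SD 0.06) to 31% (SD 0.15) with no true loss, and from 56% to 3% with a true loss of 0.05 logMAR.

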6.2.4 Objectives and hypothesis of the clinical investigation

The objective of this research study is to evaluate the safety and efficacy of the Treatment of the symptoms of Presbyopia in an implanted mono focal IOL. The Device employs a generic femtosecond laser used in numerous other ophthalmic procedures. The Device uses low levels of energy from the femtosecond laser (the "Treatment") to change an implanted monofocal lens to a bifocal.

Exclusion and inclusion criteria had been selected to allow for the most favorable outcome for the patients while allowing for standard variations in outcomes for regular cataract surgery. Multifocal IOLs are sensitive to residual astigmatism, decentration and defocus of the implanted IOL. The best outcome for the patient requires to minimize the existing aberrations.

The lens design for this study enforces for a dominant far peak and adds the second foci 2.75D. Minimizing problems due to a large diopter add or a low far diopter MTF quality.

The Sponsor has demonstrated in the prior human study that the Treatment alters the vision of the treated patient. In that study the patient's vision improved in many cases but the patient's original vision acuity was not adversely affected by the Treatment even when the Treatment was unsuccessful.

 PERFECT LENS PL-RIS01	Clinical Investigation Plan	Page no.	26 z 55
		Version	02
		Date	2023-07-18

7 Design of the clinical investigation

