7.3 Other outcome measures

The following is a list of additional outcomes measures:

- Uncorrected and corrected distance visual acuity (UDVA)
- Uncorrected and corrected intermediate visual acuity at 66 cm (UIVA)
- Uncorrected near visual acuity at 40 cm (UNVA)
- Corrected near visual acuity at 40 cm (CNVA)
- Defocus curve
- Contrast sensitivity
- Subjective refraction
- Near addition
- Slit Lamp examination findings
- Fundus examination findings
- Intraocular pressure
- Spectacle independence questionnaire

 PERFECT LENS	Clinical Investigation Plan	Page no.	27 z 55
PL-RIS01		Version	02
		Date	2023-07-18

- QoV patient questionnaire
- Treatment satisfaction
- Adverse Events
- Device deficiency

Note: All visual acuity assessment can be performed monocularly and binocularly as per the examination matrix and speciation of the measurements.

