7.18 Clinical-investigation-related procedures

7.18.1 Objective and subjective refraction

The assessment of refraction, which includes sphere (D), cylinder (D), and axis (°), will be conducted through subjective and objective methods. Objective refraction will follow standard clinical practice and will be performed by the Investigator or trained staff. Subjective testing will be conducted using trial frames instead of a phoropter. Consistency in the refractive technique should be maintained throughout the entire study duration. Test optotypes such as Sloan letters (e.g., ETDRS charts) will be used.

The cylinder value should be recorded in negative notation. Cylinder refraction should be performed for every patient. If the cylinder refraction is zero, the cylinder axis should be marked as not applicable. A pre-sign for the sphere is only necessary for negative values. If no pre-sign is entered, it indicates a positive value.

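### The Section 8.2 default summary makes no exception for refraction: applied literally, it can give an invalid axis summary and understate induced astigmatism in a non-primary outcome

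*Protocol*

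**What the plan says.** Section 8.2 is wholly descriptive: "Due to the nature of the study only descriptive statistical will be provided for the parameters in the final report". Its rule for quantitative variables reads "The default summary statistics for quantitative variables will be the number of observations (n), number of missing observations (Nmiss), arithmetic mean", followed by SD, median, minimum and maximum. Some variables get more than the default. For acuity, "The visual acuity data will be except the above mentioned characteristics also shown in cumulative frequency charts", and questionnaires have their own rules for missing values and denominators. Refraction, sphere, cylinder and axis are not mentioned in 8.2.

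Section 7.18.1 fixes the form of the data: "The assessment of refraction, which includes sphere (D), cylinder (D), and axis (°), will be conducted through subjective and objective methods". It adds that "The cylinder value should be recorded in negative notation" and that "If the cylinder refraction is zero, the cylinder axis should be marked as not applicable". Section 7.3 lists "Subjective refraction" among the additional outcome measures, and the synopsis does the same. The protocol nowhere mentions spherical equivalent, power vectors or a double-angle mean.

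Section 6.2.4 explains why the outcome matters: "Multifocal IOLs are sensitive to residual astigmatism, decentration and defocus of the implanted IOL".

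**The concern.** Axis in degrees is circular, because 0 and 180 are the same meridian. Arithmetic means, SDs and medians treat those two values as far apart. Cylinder is one part of a quantity that has both size and direction, so a summary of its size alone cannot show that the direction has changed.

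The Treatment writes a new optical element into the IOL, and Sections 6.2.1 and 6.2.2 name movement of the IOL during Treatment as the second risk. All three co-primary endpoints in 7.2 are measured with distance correction in place. That correction largely neutralises any spherocylindrical error the Treatment might cause. Manifest refraction is the direct measure of such an error, and the examination matrix (7.17) schedules the aberrometer at screening only. If refraction is summarised component by component, a change in astigmatism could go unseen in the outcome best placed to show it.

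**Working it through.** The protocol gives no mean axis, baseline cylinder or induced cylinder, so there is no figure of its own to reproduce. The form of the data comes from 7.18.1, the summary rule from 8.2 and the number of eyes (up to 24) from 8.1. Everything else is an assumption and is marked as such.

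**Axis, worked examples (arithmetic only)**
- Axes 5, 175, 10 and 170: mean = 360/4 = 90, and the median is also 90. The double-angle mean is 180.
- Six eyes at 5 and 18 at 175: mean = (30 + 3150)/24 = 132.5. The double-angle mean is 177.5.
- Six eyes at 170, 172, 174, 176, 178 and 180: mean = 1050/6 = 175, which is correct.

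The error therefore arises when eyes straddle 180, and its size depends on the split.

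**Axis, 24 eyes (assumed Normal about 180, SD 10 degrees, modulo 180; 20,000 simulated sets)**
- Arithmetic mean: median 90, 95% range 56 to 124.
- Double-angle mean: within about 4 degrees of 180 (95% range).

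**Cylinder, one eye**

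For sphere S, cylinder C and axis a: M = S + C/2, J0 = -(C/2)cos 2a, J45 = -(C/2)sin 2a. The astigmatic vector change, in cylinder dioptres, is 2·sqrt(ΔJ0² + ΔJ45²).

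Take -0.50 x 180 becoming -0.50 x 90. J0 goes from +0.25 to -0.25 and J45 stays 0, so the vector change is 2 × 0.50 = 1.00 D. Cylinder is -0.50 D at both visits. If every eye changed in this way, the cylinder mean, SD, median, minimum and maximum would all be unchanged.

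**Cylinder, mean over eyes (assumed induction at a uniformly random axis)**

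With baseline magnitude b and induced magnitude s, the mean change in magnitude is E|b + s·exp(iθ)| - b, and the share missed is 1 - (mean change)/s. At b = s = 0.50 D the mean change is 0.137 D, so the share missed is 1 - 0.137/0.50 = 73%. At b = 0.75 D and s = 0.25 D it is 1 - 0.021/0.25 = 92%.

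| Baseline cylinder | 0.25 D induced | 0.50 D induced | 0.75 D induced | 1.00 D induced |
|---|---|---|---|---|
| 0 D | 0% | 0% | 0% | 0% |
| 0.25 D | 73% | 44% | 31% | 23% |
| 0.50 D | 87% | 73% | 55% | 44% |
| 0.75 D | 92% | 83% | 73% | 60% |

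Inclusion criterion 4 in 7.6.1 sets a 0.5 D limit, but the quantity it limits is not readable in the text. If it is astigmatism (an assumption), the 0.75 D row drops out and the range becomes 0% to 87%.

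**Cylinder, fixed orientation**

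With 0.50 D at baseline and 0.50 D induced, aligned induction gives 1.00 D, so nothing is missed. Induction at 60 degrees to the baseline axis gives 0.50 D, an apparent change of zero. Induction at 90 degrees gives 0.

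**The case against.** The strongest reply is that 8.2 never says axis will be averaged. It sets a default, which allows handling by variable, and 7.18.1 governs recording, not analysis. Choosing spherical equivalent or vector components is ordinary work for a statistical analysis plan, and that plan is not shown. A reader might infer that the protocol plans to average axis. The documents do not support that, and the point is not put that way here. What remains is that the only stated rule, as worded, covers refraction and gives invalid results on an outcome the protocol itself lists, while other variables do receive special handling.

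Four further limits stand:
- A reader might infer that the mean axis would always be near 90, or that most induced astigmatism would be hidden. Both depend on distributions the protocol does not give, and several cells of the table are below half.
- Section 8.2 defines no change-from-baseline summary for refraction, so errors in an axis change score cannot be attributed to it.
- Mean spherical equivalent is not lost. It equals mean sphere plus half the mean cylinder in the same eyes, and both would be tabulated.
- Zero-cylinder eyes lose only their axis value. Their sphere and cylinder stay in the summary, although the eyes contributing to an axis summary could differ between visits.

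It would also be too strong to say that the trial could not detect a disturbed distance refraction. Uncorrected distance acuity and objective refraction are scheduled at screening and every follow-up visit, and the minimum and maximum could reveal a large cylinder in a single eye.

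**Conclusion.** The point holds in a limited form. The 8.2 default is unsuitable for axis and incomplete for cylinder, and no section makes an exception. That an arithmetic mean is unsuitable for axis, and that cylinder magnitude ignores a change of direction, needs no trial assumption. The size does: it rests on how the axes are distributed, and on assumed baseline and induced cylinder at a random axis, with 0% to about 92% missed over the grid examined.

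The consequence is confined to a non-primary outcome in a descriptive pilot of up to 12 patients. No co-primary result changes. It is a modest clarification, worth making because the protocol itself names astigmatism as relevant to multifocal performance.

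**What to change.** Add to Section 8.2:
- Axis is listed by eye and is not averaged.
- Refraction is converted per eye to M, J0 and J45, with zero cylinder giving J0 = J45 = 0.
- These are summarised as values at each visit and as within-eye change from the pre-Treatment visit.
- The magnitude of the astigmatic vector change is also summarised. It is needed alongside the signed components because induction in random directions averages to zero in J0 and J45. The signed components are needed in turn because a magnitude cannot be negative, so measurement noise alone makes its mean positive.
- The sphere and cylinder summaries and a listing of raw refractions are kept.

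The cost is a few lines of text and programming. No extra visits or measurements are needed. The small drawback is that the vector units are less familiar to clinicians, which the retained summaries and listing address.
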